In the general population physical activity (PA) is associated with beneficial effects on diseases contributing to the metabolic syndrome including reduced fat mass, and may prevent weight gain as well as maintaining body weight after weight loss, and combined with diet the effect increases [10]. High aerobic capacity has an independent prophylactic effect on comorbidities due to obesity, and greater aerobic capacity is associated with greater cardiovascular health [11]. Evidence based exercise guidelines for cardiometabolic health in people with SCI recommends a minimum of 30 minutes of moderate to vigorous aerobic exercise three times weekly to reduce cardiovascular risk factors [12]. An increased amount of PA in newly injured people with SCI is associated with more

favorable lipid profiles and increased VO₂peak during and after discharge from primary rehabilitation [13]. Changes in physical capacity during primary rehabilitation and the years after discharge has previously been described with an increase in VO₂peak of 24% during the early phase of rehabilitation, and with a further increase one year after discharge. Koppenhagen et al found that VO₂peak, despite different trajectories, increased over all in 88% of the participants during a period of 5 years [14, 15]. The course of VO₂peak during and after discharge from primary rehabilitation in a Danish context is not known. After discharge from the primary rehabilitation the amount of PA in people with SCI is varying and 50- 63 % indicates to participate in little or no sports activity on a weekly basis. The majority of those who are physical active are active at mild to moderate intensity (54% and 68% respectively) [8, 16]. Intra- and extra personal factors are influencing participation in PA, including self-efficacy related to being physically active [17]. Therefore a new paradigm is focusing on avoiding inactivity [16]. The amount and intensity of PA in people with SCI in a Danish setting is not known. An association between self-reported PA and adherence to national nutritional guidelines is not necessarily present, and therefore focus on both elements is necessary during lifestyle changes [18].

Prevention and treatment of cardiovascular risk factors

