The study consists of a primary study designed as a controlled pre-post multi modal pragmatic clinical intervention study, with 6-months of follow up and a historic control conducted as a prospective cohort study

Sub-investigations

BMI is considered a high risk determinant due to the impact of overweight on the cardiovascular risk profile and level of functioning [3]. Therefore a prospective representative longitudinal national survey of BMI is conducted in collaboration with Spinal Cord Injury Center of Western Denmark, before the onset of the controlled intervention, and serves as historic control (sub-study 1).

Additional objective outcomes measures will be collected at CSCI during the historic survey period including physical activity, physical capacity and body composition. Accordingly, two sub-studies regarding test – retest reliability of a VO₂ peak test (sub study 2) and a multi sensor accelerometer (sub study 3) respectively will be performed for two reasons. First, VO₂ peak and accelerometry are considered valid methods to measure the effect, amount and intensity of physical activity at discharge from the primary SCI rehabilitation. Secondly, these measures will be collected

repeatedly during the prospective controlled implementation study and serve as individual ¹ motivational components in the patient-clinician educative PA communication, besides being exact outcome measures. For this reason assessing the test retest reliability of the two procedures is essential (see timeline in figure 2).

Participants and eligibility criteria

All newly injured patients within the last 12 months with a SCI admitted at CSCI are included regardless of , etiology to the spinal cord lesion, neurological level or completeness* 1 of the lesion

if informed consent is retrieved and they are 18 years of age or older. In sub study 1 all newly injured people with SCI admitted at the SCI Centre of Western Denmark are also included.

Exclusion criteria for the VO2peak test in sub study 2 includes motor complete SCI (AIS A and B) at C4 level or above, and assisted ventilatory function. Other exclusion criteria are the presence of decubitus, severe spasticity or musculoskeletal problems considered at risk of aggravation during testing or preventing completion of the test.

Sub study 3 includes a convenience sample of 20 patients aiming at ensuring a broad variation of age, gender, neurological level and completeness of SCI.

Methods and analysis

Patient involvement

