The multimodal intervention will be an integrated part of usual care during the project period, and all newly injured patients will receive all the multimodal components, or parts of them, dependent on eg. the level of injury. Rehabilitation of the physical level of functioning and physical capacity will take place unchanged as usual and is a mandatory core component of highly specialized SCI rehabilitation. Therefore: decisions made by the patient during the intervention about PA, are exclusively related to PA besides the mandatory rehabilitation programme during hospitalization.

A central part of the intervention is to create a uniform and systematic approach to education of the patients about cardiovascular risk factors, PA and a healthy diet through a systematization of the existing setting and treatment interventions. In the process of preparing and reorganizing the institutional approach towards addressing cardiovascular risks, pre-education of the interdisciplinary health care personnel and peers with SCI, clarifying the roles of each profession in relation to the targeted patient education, are mandatory. Moreover, pocket cards with evidence based recommendations related to PA and diet in people with SCI are provided to all health care professionals and peers with SCI.

The patients receive information and instructions about PA and healthy diet through targeted strategic patient education based on principles that includes an individualized face to face

interaction between patients and health care professionals, while working towards, and improving a specific health related outcome through adherence to the working processes as e.g. lifestyle or medicine. [28: Møller et al. 2014; Møller et 2016].

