Patient education is generally carried out by all the health care professions in different educational settings of patients and their relatives [25, 26], with a focus on clarifying the importance of PA and a healthy diet. The overall strategic approaches to cardiovascular risk factors, beginning at the onset of the primary SCI rehabilitation and integrated into the existing setting at predetermined time points throughout the rehabilitation continuum, constitutes the aims for secondary and tertiary cardiovascular prevention. This involves training sessions [27], and feedback on physiological outcome measures and tests, that also serves as motivational tools. Additionally, a motivational conversation, goal setting meetings, tools for shared decision making [28] [24] [29], and use of mentors with SCI are also integrated as components supporting decision making about PA and healthy diet habilitation.

All components of the strategic intervention are offered the patients as a mandatory part of the systematic intervention, ensuring that information and education of the patients is provided and decisions about PA and healthy diet are made. However, the extent to which the patients engage in ie. decision making and goalsetting about PA and healthy diet) is an individual decision. Deciding not to set goals or make decisions about PA and healthy diet, is respected by the interdisciplinary health care professionals in respect of the patients autonomy.

Several outcome measures used to evaluate the intervention at admission, discharge and at follow up 6 months after discharge, are also part of the intervention as a motivational component.

In contrast to the original statistical analysis plan, not all outcomes were analyzed as intended. Therefore, in the present revised statistical analysis plan, outcomes not analyzed as intended are listed as tertiary outcomes with the intention of being analyzed in a subsequent analysis.

comprises of the following:

Primary outcome: Physical capacity (VO2peak)

Secondary outcomes: Body Mass Index (BMI), body composition, Dual- energy X-ray

Absorptiometry (DEXA),, neurological status (International

Standards for Neurological Classification of Spinal Cord Injury (ISNCSCI)),

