This study includes all patients with a new SCI hospitalized at CSCI or SCI Center of Western Denmark during a period of 10 months whereby 100 patients are expected to participate. Data concerning BMI, level of functioning (SCIM III) and neurological status (ISNCSCI) are collected at both centers. Patients with a new SCI (within the last 12 months) who are admitted for rehabilitation several months after the time of injury, are also included in the prospective survey. Therefore BMI at the time of injury is collected for all patients at admission to primary rehabilitation from both the patient's medical record and by asking the patient about weight and height at the time of injury. At CSCI, BMI every 6 week, quality of life (QoL SCI), depression (PHQ-2), amount of physical activity (Leisure Time Physical Activity Questionnaire for people With Spinal Cord Injury (LTPAQ-SCI)) and self- assessed ability to be physically active (ESES) will be collected additionally during this period, at admission, discharge and at follow up 6 months after discharge. A measure for physical capacity (VO2peak), physical activity(Actiheart multisensor accelorometer) and bodycomposition (DEXA) is performed as well at discharge. Data from this sub study serves as a historic control for the Intervention study.

Sub study 2. Test-retest reliability of a VO2 peak test

[figure not shown]
This study includes all patients participating in sub study 1 who are able of performing the test at discharge from primary rehabilitation. The patients are allocated by randomization to a test session of either intra- or interrater reliability. Four different pre -defined exercise protocols are used due to the complexity of a SCI in order to reach pre-defined criteria for VO2peak. For people with an incomplete SCI, a seated cross-trainer is used (NuStep T5XR®) with incorporated standard- and a modified test protocol in the equipment software. Equipment and modified protocol is reliable in people with traumatic brain injury and has been validated in healthy persons [33, 34]. In people with an incomplete SCI the equipment is safe, and involves a large amount of muscle mass ensuring completion of the test [35]. In case the equipment and protocols are difficult to use for

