The intervention study and follow up is performed as a pragmatic study and includes, with a few exceptions, all newly injured patients with SCI admitted to primary highly specialized rehabilitation at CSCI. Patients will be included during a time period of 18 months corresponding to approximately 50 – 60 patients. Due to the rareness of the morbidity a power calculation is not performed for the primary outcome prior to the intervention, but it is assumed that the total participant number in the intervention and in the historic control cohort, will be comparable to the existing scientific literature.

Numeric continuous data collected at admission, discharge and follow up is reported descriptively as mean and standard deviation together with 95% confidence intervals, or as median, upper and lower quartile as well as interquartile range. Changes over time is reported on the basis of paired ttest. In subproject 3 and 4 the reliability of the outcome measures is analyzed by paired t-test, Pearson's product moment correlation and coefficient of variation or Intraclass correlation coefficient between the test- retest sessions.

Recruitment of participants:

All newly injured patients who are admitted for rehabilitation at CSCI during the project period are included in the primary intervention study as it becomes a part of usual care during the project period. The patients are identified by the primary investigator through internal lists of all inpatients and future admissions. Information about the study is provided to the patients by the Ph.D student and informed consent is retrieved in order to use anonymized data relevant to the study. Likewise

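### The study is called controlled, but the Statistics section gives no estimated difference between the intervention cohort and its historic control; a paired rise in VO2peak cannot stand in for one

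*Combined protocol and SAP*

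**What the plan says.** Study Design describes the primary study as "designed as a controlled pre-post multi modal pragmatic clinical intervention study", with a historic control. The Sub study 1 section confirms the role: "Data from this sub study serves as a historic control for the Intervention study". VO2peak is the primary outcome. The Intervention section says that outcome measures taken at admission, discharge and six months after discharge are used to evaluate the intervention.

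The Statistics section gives three kinds of analysis:

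- Descriptive summaries: "Numeric continuous data collected at admission, discharge and follow up is reported descriptively as mean and standard deviation together with 95% confidence intervals", or medians and quartiles.
- Change: "Changes over time is reported on the basis of paired ttest".
- Reliability statistics for the test-retest sub-studies.

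The historic cohort appears in that section only where participant numbers are discussed. No between-cohort estimate, test, model or covariate adjustment appears there or elsewhere in the supplied text.

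**The concern.** A controlled design earns its name through a contrast with the control. Here the control cohort is recruited and measured, but the stated inferential method works inside one cohort at a time. For the primary outcome it tests whether VO2peak moved between visits.

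That matters because movement is expected anyway. The background section reports "an increase in VO₂peak of 24% during the early phase of rehabilitation, and with a further increase one year after discharge" in earlier cohorts. The Intervention section adds: "Rehabilitation of the physical level of functioning and physical capacity will take place unchanged as usual". A clear paired rise would be compatible with a useful intervention, with no effect, or with a mildly harmful one. A reader who sees a significant paired result in a study labelled controlled may credit the intervention with ordinary recovery.

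**Working it through.** **1. What each analysis estimates.** Write B for the mean VO2peak change that would occur without the intervention, D for the intervention effect, and K for the net difference between cohorts in case mix, calendar time and test practice.

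- Paired change in the intervention cohort estimates B + D.
- Difference in discharge VO2peak between cohorts estimates D + K. Adjustment for measured covariates aims to shrink K.

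The plan specifies the first and not the second. If B were the cited 24% and D were zero, the expected paired change would be 24%. This is an illustration only: the care those earlier cohorts received is not described, and the protocol says the Danish course of VO2peak is not known. The argument needs only that B is plausibly not zero.

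**2. Whether control data exist.** The Sub study 1 section places control VO2peak and DEXA at discharge, at CSCI. The Outcome measures section says generally that all outcomes are collected at admission, discharge and six months. The timeline figure is not available here. Under either reading, discharge VO2peak can be compared. Whether change from admission can be compared depends on how the two statements are reconciled.

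**3. How many controls.** The documents give no count of controls with a VO2peak test, so these are assumptions.

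- Upper bound: 70 CSCI admissions a year over 10 months, 70 × 10/12 = 58, with no losses. The 100 expected in sub-study 1 covers both centres, and VO2peak is described for CSCI only.
- Same yield as the Statistics section, with its 18 months read as intake: 50 × 10/18 = 28 and 60 × 10/18 = 33.
- Same yield with 12 months of intake, since the primary-study section counts the six-month follow-up within its 12 to 18 months: 50 × 10/12 = 42 and 60 × 10/12 = 50.
- Low scenario of 20, if many cannot be tested or are excluded. This has no source figure.

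Thirty tested intervention patients is likewise an assumed low case.

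**4. Precision of an unadjusted comparison.** In SD units, half-width = t(0.975, n1 + n2 − 2) × √(1/n1 + 1/n2). For 60 versus 58: 1.981 × √(1/60 + 1/58) = 1.981 × 0.184 = 0.365. The detectable difference is for 80% power, two-sided 0.05, two-sample t (noncentral t).

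| Intervention | Control | 95% CI half-width (SD) | Detectable difference (SD) |
|---|---|---|---|
| 60 | 58 | 0.365 | 0.52 |
| 50 | 58 | 0.383 | 0.55 |
| 60 | 50 | 0.380 | 0.54 |
| 50 | 42 | 0.416 | 0.59 |
| 60 | 33 | 0.430 | 0.61 |
| 50 | 28 | 0.470 | 0.67 |
| 60 | 20 | 0.514 | 0.73 |
| 50 | 20 | 0.528 | 0.75 |
| 30 | 20 | 0.580 | 0.83 |

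The plan reports no power calculation, effect size or SD, so there is no figure of its own to reproduce. Precision of the adjusted analysis depends on a residual variance that is not known.

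**The case against.** Four points can be made for the plan.

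*The aim is implementation.* The Objectives section speaks of developing and implementing an approach, and adoption by staff has its own 75% agreement rule. This softens the point but does not remove it. The background identifies a gap on efficacy and effectiveness, the primary study aims to decrease cardiovascular risk, and the design is called controlled.

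*The summaries already cover both cohorts.* By-visit means with 95% intervals, reported for each cohort at discharge, would allow a side-by-side look. That stands, so it would be wrong to say the plan allows no comparison at all. Two separate intervals are still not an estimated difference, and they are not adjusted.

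*Historic comparisons are confounded.* True, and adjustment will not cure it. The paired test, however, leaves expected recovery wholly unaddressed.

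*The analysis may be done.* The revised plan states "In contrast to the original statistical analysis plan, not all outcomes were analyzed as intended". Anything added now is post hoc.

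Stronger readings are tempting but unsupported. A reader might infer that a significant paired result would be a false positive. It would not: rejecting no change is correct if VO2peak rose, and the error lies in attributing the rise. A reader might take 24% as the usual-care rise at this centre, but the documents do not say so. A reader might conclude that controls have no admission VO2peak, but the Sub study 1 and Outcome measures sections conflict on this. Nor does the text show that no comparison was ever made, only that none is specified.

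**Conclusion.** The concern holds and should be fixed before VO2peak results are interpreted. The stated test answers a different question from the one the controlled design poses. Followed as written, the plan yields no estimate that separates an intervention effect from recovery under continuing rehabilitation.

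Confidence is high for the omission, which rests on the text and on no assumed SD. It is lower for what the remedy can deliver. With about 50 to 60 intervention patients and 28 to 58 controls, an unadjusted difference of roughly 0.5 to 0.7 SD is what could be detected with 80% power, and smaller effects may be missed. Those control numbers are assumptions. The remedy gives a comparison with the earlier cohort, not secure attribution.

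**What to change.** Add a dated SAP revision, labelled post hoc, containing:

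1. **Primary comparison.** Linear regression of discharge VO2peak on cohort (intervention versus CSCI historic control), reporting the difference with its 95% CI. Adjust for admission AIS grade and tetra-/paraplegia and, where recorded in both cohorts, age, sex and time since injury. Use admission AIS because neurological status is also an outcome.
2. **Comparable testing.** State one rule for which test counts in both cohorts, since controls in the reliability sub-study may have up to three. Apply the same test exclusions to both cohorts, report the number not tested in each, and show results with and without adjustment for test device and protocol.
3. **Other outcomes.** Treat discharge DEXA the same way. Compare BMI, LTPAQ-SCI and ESES with a cohort-by-time model in CSCI patients.
4. **Labelling.** Present the paired t-tests as within-cohort change, not as evidence of intervention effect.
5. **Timing.** Reconcile the Sub study 1 and Outcome measures sections on when control VO2peak was measured. If admission values exist, add them as a covariate.
6. **Limits.** State that confounding by calendar time, case mix and test practice remains; practice matters if only intervention patients were also tested at admission.

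The cost is a plan revision and a few regression models, mostly on data the plan already provides for. Availability of age, sex and time since injury in both cohorts needs checking, because they are not listed explicitly as data items. The downside is the limited precision shown above, and a result that must be reported as post hoc.
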